### **3.1.1      Screening Period**

Prospective subjects will be assessed during a Screening Period of up to 4 weeks to confirm initial eligibility for the study via medical history, physical examination, review of prior therapy, clinical laboratory tests, and esophagogastroduodenoscopy (EGD), for evaluation of histologic and endoscopic findings. For the EGD and informed consent only, an extension of the screening window of up to 8 weeks total may be allowed to accommodate the scheduling of this procedure after informed consent has been obtained. The screening EGD must be performed within 8 weeks (56 days) of the planned Day 1 Visit for subjects to be eligible to participate in the study. All screening procedures should be performed during the 4-week Screening Period prior to Day 1. Symptoms of EGE will be assessed by the patient-reported outcome (PRO) questionnaire (referred to as Izumo Scale [weekly], [REDACTED]

[REDACTED]. Izumo scale will be completed at least the 2 consecutive weeks before the IP administration on Day 1, but may be performed for consecutive weeks during the screening period. [REDACTED]

Refer to [Section 6.1](#)

for further details.

### **3.1.2      Induction Phase**

Following a 4-week Screening Period, subjects meeting all inclusion criteria and none of the exclusion criteria will be eligible for enrollment in the Induction Phase. Approximately 45 subjects 12 to 75 years of age, inclusive, with a diagnosis of EGE and with symptoms of EGE will be randomized 2:1 to receive CC-93538 360 mg SC once weekly (N = approximately 30) or matching placebo (N = approximately 15), in a double-blind fashion for 16 weeks. Subjects will be required to have weekly symptom scores of  $\geq 4/15$  for any of Gastric Pain Symptoms domain, Stomach Heaviness Symptoms domain and /or Diarrhea Symptoms domain, as assessed by the Izumo Scale with electronic device over the 2 consecutive weeks before baseline (assessed on Day 1), and histologic evidence of EGE with  $\geq 30$  eos/hpf in at least 5 hpf in the stomach and/or  $\geq 30$  eos/hpf in at least 3 hpf in the duodenum. Both assessments will be conducted while on stable background therapy. Peak gastric/duodenum eos count will be confirmed by the central reader.

Subjects weighing  $\geq 30$  kg will be enrolled in this study. Currently, there is no administration experience of CC-93538 360 mg once weekly in subjects weighing  $< 40$  kg. Careful and close safety monitoring (eg, for hypersensitivity reaction) should be considered for this population. For subjects weighing  $\geq 30$  kg and  $< 40$  kg, the first 3 weekly SC doses will be administered in the

clinic, with confirmation of concomitant medications and AEs, and those subjects will remain in the clinic for at least 1 hour following dosing for observation, and be monitored every 2 weeks by the site staff by telephone (but not limited to telephone) between regularly scheduled visits until Week 16 (ie, Week 6 [Day 43 ± 3 days], Week 10 [Day 71 ± 3 days], and Week 14 [Day 99 ± 3 days]).

Treatment assignment at baseline will be stratified by (with/without) concomitant use of corticosteroid treatment at baseline (up to 10 mg/day as the equivalent of prednisone) to ensure an equal balance in the treatment arms. Baseline assessments and procedures will be completed prior to randomization and administration of IP on Day 1. The dosage regimen of permitted anti-inflammatory therapy (including concomitant corticosteroid treatment at baseline; up to 10 mg/day as the equivalent of prednisone) must be kept stable until Week 16. Subjects with a worsening of EGE symptoms (described in [Section 6.4.2.10](#)) during the Induction Phase will be required to complete the EGE Flare Assessment Visit per the Table of Events ([Table 4](#)). The subject may continue to participate with concomitant rescue therapy as needed and will be eligible to enter the OLE Phase following completion of Week 16 of the Induction Phase, or discontinue from the study. Details are described in [Section 3.1.6](#). All attempts should be made to complete the Induction Phase.

Clinical laboratory tests, vital signs, physical examinations [REDACTED]  
pregnancy tests (female of childbearing potential [FCBP] subjects only), EGD, clinical symptom assessment, subject-reported outcomes, serum CC-93538 PK concentrations, serum antibodies to CC-93538 (to assess immunogenicity), concomitant medications, and AE/SAE assessments will be performed according to the Table of Events presented in [Table 4](#). [REDACTED]  
[REDACTED]

### **3.1.3 Maintenance Phase**

After completion of Week 16 of the Induction Phase, eligible subjects will continue participation and enter the Maintenance Phase if none of the conditions disqualifying subjects from eligibility have been met as described in [Section 3.1.6](#). A placebo-controlled Maintenance Phase will allow for a determination of persistence of treatment effect and the overall long-term efficacy of CC-93538.

The Maintenance Phase treatment arms include CC-93538 360 mg SC once every week, CC-93538 360 mg SC once every other week, and matching placebo. Subjects who are randomized to receive CC-93538 360 mg SC once weekly in the Induction Phase will be re-randomized (1:1) to CC-93538 360 mg SC once weekly or CC-93538 360 mg SC once every other week at the beginning of the Maintenance Phase, and subjects who are randomized to receive matching placebo in the Induction Phase will continue placebo in the Maintenance Phase. A double-blind fashion will be kept in the Maintenance Phase.

If the reduction of EGE-related symptoms is observed at/after Week 16 (in the Maintenance Phase), the investigator should begin tapering the dosage regimen of concomitant corticosteroid treatment after Week 16. The dose reduction should be 2.5 mg/week (as the equivalent of prednisone). If the symptoms worsen after tapering of the dosage regimen of concomitant

corticosteroid treatment, the dose can be increased until it is the same as the baseline dose at the Induction Phase.

Subjects who complete Week 48 of the Maintenance Phase have 2 options:

1. to enter the Open-label Long-term Extension Phase (Section 3.1.4)
2. to return for an Interim and a Final Safety Follow-up Visit at 8 and 16 weeks, respectively, after the last dose of IP (at Week 55 and Week 63 for study completers) ([Section 3.1.5](#))

Subjects with a worsening of EGE symptoms (described in [Section 6.4.2.10](#)) during the Maintenance Phase will be required to complete the EGE Flare Assessment Visit per the Table of Events ([Table 5](#)). The subjects will need to discontinue participation in the Maintenance Phase and may be eligible to enter the OLE Phase. Details are described in Section 3.1.6.

Clinical laboratory tests, vital signs, physical examinations [REDACTED]  
pregnancy tests (FCBP subjects only), EGD, clinical symptom assessment, subject-reported outcomes, serum CC-93538 PK concentrations, serum antibodies to CC-93538 (to assess immunogenicity), concomitant medications, and AE/SAE assessments will be performed according to the Table of Events presented in [Table 5](#). [REDACTED]  
[REDACTED]

The study blind should be maintained for persons responsible for the ongoing conduct of the study (after all subjects have completed the Week 48 assessments for endpoint analysis). Blinded persons may include but are not limited to: the Clinical Research Physician (also referred to as Clinical Trial Physician), Clinical Research Scientist, Clinical Trial Manager, Study Statistician, Data Manager, Programmers, and Clinical Research Associates.

### **3.1.4      *Open-label Long-term Extension Phase***

Subjects who meet one of the following criteria with respect to participation in the Induction Phase and the Maintenance Phase will be given the opportunity to participate in the OLE Phase.

- Subjects who do not qualify for entry into the Maintenance Phase including:
  - Subjects who experience a severe EGE flare requiring concomitant rescue therapy during the Induction Phase will be eligible for the OLE Phase after completion of Week 16 of the Induction Phase
- Subjects who cannot complete the Maintenance Phase including
  - Subjects who experience a severe EGE flare requiring concomitant rescue therapy and/or worsening of EGE symptoms (for 2 consecutive visits [4 weeks apart] at the beginning of or during the Maintenance Phase will be eligible to enter the OLE Phase at the Early Termination (ET) Visit
- Subjects who complete Week 48 of the Maintenance Phase will be eligible for the OLE Phase after completion of Week 48 of the Maintenance Phase.

The OLE Phase baseline assessments will be obtained from either the Induction Phase Week 16 Visit assessments, the Maintenance Phase Week 48 Visit assessments, or the Maintenance Phase

EGE Flare Assessment Visit, and ET Visit assessments, as applicable. Additional OLE baseline assessments not performed at the final Induction Phase Visit (Week 16), final Maintenance Phase Visit (Week 48) or the Maintenance Phase EGE Flare Assessment Visit and ET Visit assessments should be conducted at the OLE Day 1 Visit in accordance with the Table of Events ([Table 6](#)); it is anticipated that this should occur for most subjects on the same day. Subjects will not be allowed to enroll in the OLE Phase and receive IP on OLE Day 1 if there will be a delay of > 21 days from dosing in the final Induction Visit or the final dosing in the Maintenance Phase unless discussed with the Medical Monitor (refer to [Section 6.3.2](#)). The 2 Safety Follow-up Visits are not required for subjects enrolling in the OLE Phase, after the final Induction Phase Visit, final Maintenance Phase Visit or the Maintenance Phase EGE Flare Assessment Visit and ET Visit assessments.

During the OLE Phase, all subjects will be administered CC-93538 at a dose of 360 mg SC once weekly as long as they are participating in the study, until the investigator decides to withdraw the subject, or the Sponsor decides to terminate/complete the study. Individual subject participation in the OLE Phase may be for a minimum of 2 years but may extend for a longer duration. The dosing regimen in the OLE Phase may be revised through an amendment to the study protocol once results from the Maintenance Phase are available and the most effective and safest dosing regimen is confirmed.

Depending on the EGE symptoms of subject, the investigator may decrease/increase the dose of concomitant corticosteroid treatment after OLE Visit 1 during the OLE Phase.

Subjects with a worsening of EGE symptoms (described in [Section 6.4.2.10](#)) during the OLE Phase will be required to complete the EGE Flare Assessment Visit per the Table of Events ([Table 6](#)).

Clinical laboratory tests, vital signs, physical examinations [REDACTED]  
pregnancy tests (FCBP subjects only), EGD, clinical symptom assessment, subject-reported outcomes, serum CC-93538 PK concentrations, serum antibodies to CC-93538 (to monitor for immunogenicity), concomitant medications, AE/SAE assessments, [REDACTED]  
[REDACTED] will be performed in accordance with the Table of Events ([Table 6](#)).

Subjects may discontinue from the OLE Phase at any time. Subjects who discontinue the study at or after 2 years of participation (the fourth quarter Visit in Year 2 [Week 104]) will complete an OLE-End of Treatment (EoT) Visit within 2 weeks after receiving the final dose of CC-93538, and an 8-week Interim and a 16-week Final Safety Follow-up Visit at 8 weeks and 16 weeks, respectively, after the final dose of CC-93538 for the assessment of safety and clinical status. Subjects who discontinue the study before Week 104 will complete an OLE-ET Visit ([Table 6](#)).

### **3.1.5 Early Termination, End of Treatment and Safety Follow-up Visits**

Subjects who complete Week 48 of the Maintenance Phase and do not participate in the OLE Phase will be required to return for an Interim and a Final Safety Follow-up Visit at 8 and 16 weeks, respectively, after the last dose of IP (at Week 55 and Week 63 for study completers). Subjects may discontinue from the study at any time. Subjects who discontinue the study during the Maintenance Phase will complete ET Visit and subjects who discontinue the study during the OLE Phase (and before OLE Week 104) will complete an OLE-ET Visit within 2 weeks after their final

dose of IP. In addition to the ET or the OLE-ET Visit procedures, subjects exiting the study early will also return for the Interim and the Final Safety Follow-up Visits ([Section 6.3.1](#)). However, subjects who are permanently discontinued from IP and continue study participation in order to complete safety and efficacy assessments will return for the Interim and Final Safety Follow-up Visits after their last study visit (refer to [Section 6.3.1](#)).

For subjects who discontinue the study at or after 2 years of participation (the fourth quarter visit in OLE Phase Year 2 [OLE Week 104]) will complete an OLE-EoT Visit ([Section 6.2.2](#)) within 2 weeks after their final dose of IP and an 8-week Interim and a 16-week Final Safety Follow-up Visit.

### **3.1.6      *Worsening of EGE Symptoms and EGE flare***

Subjects with a worsening of EGE symptoms (described in [Section 6.4.2.10](#)) during the study, either in the Induction Phase, Maintenance Phase, or the OLE Phase will be required to complete the EGE Flare Assessment Visit per the Table of Events ([Table 4](#), [Table 5](#), and [Table 6](#)). For subjects with a worsening of EGE symptoms and/or EGE flare, an EGD may be required to determine if rescue therapy is clinically indicated. The results of the gastric/duodenal eos count will be blinded to investigative sites with the possible exception of screening during the Induction Phase (see below). After randomization, a local histologic assessment of EGD biopsy samples should not be performed, unless required for safety reasons (eg, severe EGE flare, etc).

Any worsening of EGE symptoms during study participation will be documented as an EGE flare. See [Section 6.4.2.10](#) and [Section 6.2.1](#) for the protocol definition of EGE flare and EGE Flare Assessment Visit details, respectively.

Subjects with increased signs and symptoms of EGE are instructed to contact the investigator and/or study staff to determine if an EGE Flare Assessment Visit is warranted.

#### Induction Phase

Subjects experiencing a severe EGE flare and/or worsening of EGE symptoms (for 2 consecutive visits [4 weeks apart], described in [Section 6.4.2.10](#)) in the Induction Phase may continue to participate with concomitant rescue therapy as needed and will be eligible to enter the OLE Phase following completion of Week 16 of the Induction Phase. Subjects with a severe EGE flare in the Induction Phase will not qualify for entry into the Maintenance Phase.

If the gastric/duodenal eos count is required to determine the need for emergent rescue therapy during the Induction Phase, the results of the gastric/duodenal eos count will be disclosed as long as the investigator requires the result. The subject is to be discontinued from the study and will not be allowed to enter either the Maintenance Phase or the OLE Phase. All attempts should be made to complete the Induction Phase.

Subjects experiencing a mild to moderate EGE flare in the Induction Phase will continue to the Maintenance Phase of the study.

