### **9.3 Sample Size and Power Considerations**

The sample size is based on two-sample t-test for the primary endpoint, changes in mean number of peak eos per hpf in GI biopsies from baseline to Week 16. The null hypothesis and the alternative hypothesis for the primary endpoint are as follows;

- Changes in mean number of peak eos from baseline at Week 16

Null hypothesis  $H_0: \mu_{CC-93538} = \mu_{Placebo}$

Alternative hypothesis  $H_a: \mu_{CC-93538} \neq \mu_{Placebo}$ ,

where  $\mu_{CC-93538}$  represents the true mean change value relative to CC-93538 and  $\mu_{Placebo}$  represents true mean change value relative to placebo.

Using this hypothesis, if the expected mean change in eos count in the active treatment group was -70, the expected mean change in eos count in the placebo group was 0, and the standard deviation (SD) was 70, the sample size necessary to achieve at least 80% power in a t-test at a significance level of 0.05 was calculated. Using a 2:1 ratio of active to placebo, 39 subjects are required. Assuming a Week 16 drop-out rate of approximately 10%, the goal is to enroll a total of 45 subjects.

The expected change from baseline in eos count in the active treatment group is based on the Phase 2 EoE study (Study RPC02-201); mean value at baseline for the CC-93538 360 mg treatment group of 139.4, and mean value at Week 16 of 31.3, with a percent change of approximately 80%. The baseline value in patients with EGE was assumed to be approximately 90 based on the results of studies of other drugs in patients with EGE (Dellon, 2020). Therefore, the expected change from baseline in eos in the active treatment group is assumed to be approximately 70. Change from baseline in eos count in the placebo group was assumed to be 0 based on the results of studies of other drugs (Dellon, 2020). With reference to the baseline GI eos count results of other drug studies of 52 (Dellon, 2020), the results of Study RPC02-201 in the CC-93538 360 mg group of 90, and the results of Study RPC02-201 in the CC-93538 180 mg group of 71, SD was assumed to be 70, which is approximately the mean of those values.

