## **9.6 Efficacy Analysis**

### **9.6.1 Efficacy Analysis of the Primary Endpoint**

#### **9.6.1.1 Intercurrent Event and Analysis Strategies**

The following are the intercurrent events (ICEs) of interest:

1. Treatment discontinuation in subjects without the use of concomitant rescue therapy or prohibited medication (subjects remain in the study)
2. The use of concomitant rescue therapy or prohibited medication which may impact the efficacy assessment for CC-93538
3. Treatment discontinuation followed by rescue therapy or prohibited medication which may impact the efficacy assessment for CC-93538

For intercurrent event (ICE) number 1, all observed data will be included in the primary analysis regardless of the occurrence of the ICE according to the respective endpoint definition. For ICE numbers 2 and 3, all observed data will be included in the primary analysis.

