#### **9.6.1.2 Changes in Mean Number of Peak eos Count from Baseline to Week 16 (Induction Phase)**

The primary analysis will be conducted on the ITT population based on an analysis of covariance (ANCOVA) model with treatment group, concomitant steroid use (yes or no), and baseline eos count included in the model. The comparison between CC-93538 360 mg SC once weekly and placebo for change in number of peak eos count from baseline at Week 16 will be made using the difference in least squares mean (LSM) at a 5% 2-sided significance level. Point estimates for the mean difference between the two treatment groups using the LS mean changes and corresponding 95% Wald CI will be reported. In addition, LSMs (standard error [SE]), arithmetic means (SD), and arithmetic mean changes (SD) will be summarized by treatment group.

Missing data will be handled using a multiple imputation (MI) approach under a missing at random (MAR) assumption.

Sensitivity analyses will be performed to support the primary analysis and provide additional insights to understand the treatment effect. For the primary estimand analysis, robustness due to missing data MI under MAR assumption will be explored using tipping point analysis ([Yan, 2009](#); [Campbell, 2011](#); [Yuan, 2014](#)). In considering the ICEs of study interest (ie, ICE number 2, use of rescue therapy/prohibited medication, and ICE number 3, treatment discontinuation followed by use of rescue therapy/prohibited medication), an analysis using the hypothetical estimand strategy for change in eos count at Week 16 will be conducted.

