## 11 DISCONTINUATIONS

### 11.1 Treatment Discontinuation

The following events are considered sufficient reasons for discontinuing a subject from the IP(s):

- Adverse event
- Physician decision
- Lack of efficacy
- Protocol deviation that may impact subject safety
- Withdrawal by subject or parent/guardian
- Death
- Lost to follow-up
- Non-compliance with IP
- Other (to be specified on the eCRF)

The following events require permanent discontinuation of IP:

- Pregnancy
- An SAE which is suspected of being related to IP
- Anaphylactic reaction or other severe systemic reaction (eg, hypersensitivity, allergic, or autoimmune) suspected of being related to IP
- Malignancy diagnosis, excluding carcinoma in situ of the cervix or squamous or basal cell carcinoma of the skin if it can be successfully treated by local resection
- Presence of an opportunistic infection suggestive of immunocompromise
- The following severe laboratory abnormalities suspected of being related to IP (laboratory indices should be repeated for confirmation prior to permanent IP discontinuation, within 48 to 72 hours after the abnormality was first observed):
  - Neutrophil count  $\leq 0.5 \times 10^3/\mu\text{L}$
  - Platelet count  $\leq 50 \times 10^3/\mu\text{L}$
  - ALT and/or AST values  $> 3 \times \text{ULN}$  with total bilirubin  $> 2 \times \text{ULN}$  or INR  $> 1.5$ , excluding confirmed Gilbert Syndrome or therapeutic anticoagulation
  - ALT and/or AST  $> 5 \times \text{ULN}$  for greater than 2 weeks duration
- 3 or more consecutive missed doses, unless in consultation with the Medical Monitor it is determined that despite 3 or more consecutive missed doses it is in the best interest of the subject to continue participation with the possibility of re-starting CC-93538 at an appropriate time in the future
- Disclosure of the results of the gastric/duodenal eos count (in Induction Phase only)
- Use of systemic immunosuppressive or immunomodulating drugs prohibited per protocol (see [Section 8.2](#))

Note: INR is part of the coagulation panel and may be obtained at the discretion of the investigator via central or local laboratory testing.

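### The protocol contradicts itself on whether an Induction subject whose eosinophil count is disclosed to decide on rescue stays for the Week 16 assessments, so the primary endpoint may go missing for a reason related to outcome

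*Combined protocol and SAP*

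**What the plan says.** Section 3.1.6 (Induction Phase) covers the case where the gastric or duodenal count is needed to decide on emergent rescue. The count may then be disclosed, with this consequence: "The subject is to be discontinued from the study and will not be allowed to enter either the Maintenance Phase or the OLE Phase". The sentence that follows is "All attempts should be made to complete the Induction Phase".

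Section 11.1 has a list of events that require permanent discontinuation of investigational product. One entry reads "Disclosure of the results of the gastric/duodenal eos count (in Induction Phase only"). The text after the list encourages subjects taken off product to stay for the remaining assessments of that phase, efficacy included. It then says that those who stop product in Induction leave the study.

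On analysis, 9.6.1.1 treats rescue, and treatment discontinuation followed by rescue, as intercurrent events 2 and 3: "For ICE numbers 2 and 3, all observed data will be included in the primary analysis". Section 9.6.1.2 fills missing Week 16 values by multiple imputation under missing-at-random (MAR) and adds a tipping-point analysis. Severe flares managed without disclosure may stay to Week 16 with rescue (3.1.6).

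**The concern.** The primary strategy uses whatever is observed after rescue. It works only if the Week 16 biopsy is taken in rescued subjects. If disclosure ends study participation, the protocol stops collecting that value in a group defined by worsening and possible need for rescue. The value then has to be imputed, and MAR is hard to defend when withdrawal was triggered by the course of the disease. The tipping-point analysis can show how far the result depends on MAR, but it cannot recover a measurement that was never taken.

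Two sites could follow the protocol in good faith and differ on whether a Week 16 biopsy exists. With about 15 placebo subjects, each one carries about 1/15 of that arm's mean, and the trial has a single formal test.

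**Working it through.** **1. The plan's own sample size.** Inputs from 9.3: mean change -70 on active and 0 on placebo, SD 70, 2:1 allocation, power at least 80%, alpha 0.05 ("the sample size necessary to achieve at least 80% power in a t-test at a significance level of 0.05 was calculated"). The test is two-sided according to 9.6.1.2 ("difference in least squares mean (LSM) at a 5% 2-sided significance level"). Power comes from the noncentral t with noncentrality 70 / (70 × √(1/n_placebo + 1/n_active)).

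- 12 + 24 = 36 subjects: 78.5%
- 13 + 26 = 39 subjects: 81.8%, so 39 is the smallest 2:1 total that reaches 80%
- 39 / 0.9 = 43.3, hence 44; the next multiple of three is 45

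The stated 39 and 45 reproduce, and nothing below changes them.

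**2. The passages side by side.**

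| Place | Disclosed Induction subject |
|---|---|
| Protocol Summary, 6.2, 6.3.2, 6.4.2.10 | leaves the study |
| 7.2.11 | withdrawn from the study, set against other rescued subjects who may continue |
| 3.1.6 | leaves the study; the next sentence asks for completion of Induction |
| 7.2.10 (applies to every event listed in 11.1) | off product, encouraged to complete the phase |
| 11.1 | off product, encouraged to complete the phase; also discontinued from the study |
| 11.2 | 11.1 events end study participation; a note then encourages those not discontinued from the study to complete the phase |

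Intercurrent event 1 in 9.6.1.1 is defined for subjects who stop treatment but remain in the study, so the estimand presumes that such retention is possible.

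**3. Possible shift in the estimate.** Let f_a and f_p be the shares of the active and placebo arms with no Week 16 value, and D the true change minus the imputed change, taken as equal in both arms. For the difference active minus placebo (negative favours the drug):

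true difference − MAR difference = D × (f_a − f_p)

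The documents give neither a disclosure rate nor a value for D. As an illustration, assume 1 to 3 of 15 placebo subjects are lost and D is 60 eos/hpf in size:

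- 60 × 1/15 = 4 and 60 × 3/15 = 12 eos/hpf; divided by 70, that is 5.7% to 17.1%
- D = -60 (rescue lowers counts below the imputed value): MAR overstates the drug effect by 4 to 12
- D = +60 (counts end above the imputed value): MAR understates it by 4 to 12
- 2 placebo and 4 active lost: 4/30 − 2/15 = 0, no shift
- active losses only: 60/30 = 2 eos/hpf per subject, with the two directions exchanged

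**4. Scale.** The SE at 45 subjects is 70 × √(1/15 + 1/30) = 22.1, so 4 to 12 eos/hpf is 0.18 to 0.54 SE. The smallest significant difference is about 44.6 (t on 43 df). To bring an estimate of -70 back to -44.6:

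- three placebo losses would each have to be mis-imputed by 25.4 / (3/15) = 127 eos/hpf, more than the assumed mean baseline of about 90
- one to four active losses would each have to be mis-imputed by about 761 to 190 eos/hpf

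These figures ignore between-imputation variance and covariate adjustment.

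**5. Power.** With all 45 observed, power is 87.1%. Losing 3 placebo and 2 active subjects leaves 80.6%; losing 4 and 2 leaves 78.1%.

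**The case against.** The strongest reply is that the text can be read consistently: the subject finishes the Induction assessments off drug and then leaves instead of entering a later phase. The second sentence in 3.1.6, 7.2.10 and the encouragement in 11.1 support this. So does 6.3.1, which times safety follow-up from the last study visit for subjects who stay off product. On that reading the Week 16 biopsy is collected and nothing is lost. This reading is available, but the text does not require it. The Protocol Summary and 7.2.11 present leaving the study as the alternative to continuing in the phase, and 11.2 says the listed events end study participation.

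Four stronger readings are tempting, and the documents do not support them:

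- *Section 11.1 only stops drug, so it conflicts cleanly with 3.1.6.* It also says that subjects who stop product in Induction are discontinued from the study, and 11.2 agrees. The conflict lies within 3.1.6, 11.1 and 11.2 as much as between them.
- *The most severe flares lose the endpoint.* The trigger is that the count is needed to decide on rescue. Severe flares rescued without disclosure may stay, and loss of the endpoint is possible, not certain.
- *Missing values would be imputed from subjects who did not flare.* Rescued subjects who stay contribute observed data. The variables in the imputation model are not given. Table 4 provides for an EGD at the flare visit and for an early-termination EGD from Week 8, but the documents do not say whether the imputation uses either, and neither is a Week 16 value.
- *The drug effect is overstated by 6% to 17%.* That requires losses in placebo only and a strong response to rescue. Three of 15 is 20%, twice the planned drop-out, and the sign reverses if counts end above the imputed value.

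It also stands that the tipping-point analysis already examines departures from MAR, and that the 10% allowance covers about five losses if no one else drops out.

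**Conclusion.** The contradiction is real and bears on collection of the primary endpoint. Under the withdrawal wording, the Week 16 count would be missing for a reason related to outcome. The analysis would then depart from the declared strategy of using data observed after rescue, and MAR would be doubtful for these subjects.

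Size and direction are unknown, because no disclosure rate, arm split or post-rescue change is given. The 4 to 12 eos/hpf either way is an illustration that rests on 1 to 3 placebo losses and an imputation error of 60. At the planned effect of 70, shifts of that order would disturb the estimate rather than overturn the test. This is a point about the estimand and avoidable missing data, not about power or the stated sample size.

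**What to change.** Reconcile the Protocol Summary and Sections 3.1.6, 6.2, 6.3.2, 6.4.2.10, 7.2.10, 7.2.11, 11.1 and 11.2. The rules on treatment, rescue and entry to later phases are for the sponsor to settle, and this point takes no position on them.

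Whatever those rules are, state that disclosure alone does not end collection of the scheduled Week 16 assessments, including the centrally read biopsy. Make this subject to the subject's consent and to the existing exception in 6.2.1 for a flare EGD judged too recent to repeat safely. The data then enter the ITT analysis as 9.6.1.1 intends.

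The cost is amendment wording. The Week 16 EGD is already scheduled, 6.2.1 already keeps it after a flare EGD, and central reading is blinded to treatment (6.4.1), so disclosing a count to a site does not affect that blinding. The downside is small: some of these subjects would have the scheduled Week 16 EGD after a flare EGD.
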